### A) NURSE INTERVENTION:

The recommended core treatment elements of the current EULAR and BSR recommendations form the basis of the nurse-led intervention (7, 8). These key elements have been incorporated into a management package suitable for implementation in community-based clinical practice. This package was developed during phase 1 of the study which included qualitative interviews of patients exploring illness perceptions and possible barriers to care. The nurse led package of care will be individualised according to the characteristics and needs of the participant and will include elements of the following:

- (1) a clear verbal explanation of gout backed up by written information (Arthritis Research UK patient booklet). The explanation will include the following key messages:
  - we know its cause it is due to deposition of urate crystals in and around peripheral joints
  - crystals form when SUA levels rise above the critical "saturation point" for crystal formation
  - in people with persistently raised SUA crystals slowly accumulate without causing symptoms
  - when sufficient crystals have formed in cartilage some occasionally "spill out" into the joint cavity, triggering severe inflammation of the joint lining and presenting as an acute attack of gout
  - "shed" crystals are largely dissolved by the inflammation so the attack settles
  - over many years acute attacks may increase in frequency and spread to involve other joints
  - in addition to acute attacks, continuing deposition may eventually result in hard, slowly expanding lumps of crystals ("tophi") that can cause pressure damage to joint cartilage and bone and even appear as palpable lumps under the skin
  - in some people tophi may result in irreversible joint damage (i.e. osteoarthritis) and cause regular chronic pain on using the joints
  - reduction and maintenance of SUA levels below the saturation point (1) stops production of new crystals and (2) encourages existing crystals to dissolve – so eventually there are no crystals and therefore no gout
- (2) an individualised explanation of relevant risk factors that elevate uric acid above the saturation point (basically too much production, or insufficient elimination of uric acid) including:
- hereditary factors that result in some people having relatively inefficient renal excretion of urate
- a high body mass the majority (2/3) of uric acid being made by the body's cells by breaking down purines into uric acid, releasing energy for the cells
- a diet containing plenty of foods that are high in purines (1/3 of uric acid comes from the diet)
- drugs (such as diuretics) that reduce the kidney's ability to excrete uric acid
- chronic renal impairment associated with ageing or kidney disease.
- (3) individualised advice on management of an acute attack (selecting from ice packs, oral colchicine, oral NSAID plus PPI, corticosteroid)

Page **16** of **29** Final version 8 –18 May 2015

- (4) individualised advice on ways to reduce uric acid levels by lifestyle modification, if this is appropriate (e.g reducing weight if overweight or obese, reduction in excessive beer intake, dietary alteration)
- (5) advice on ULT (in line with current recommended guidelines), including initiation of new ULT, with an upward titration regimen (with approximately one month between each incremental increase in ULT) and allopurinol the first-line drug to consider (febuxostat, sulphinpyrazone, benzbromarone also considered as appropriate). Prescriptions for ULT will be signed by [name] and issued through Nottingham City Hospital pharmacy.

The nurse will follow up the patient at variable time intervals as appropriate to the needs of the patient. It is envisaged that visits will be most frequent (e.g. monthly) in the first 6 months when ULT is being initiated and titrated upwards; subsequently visits may reduce to 3, 6 or 9 monthly depending on difficulty of gout management. Telephone contact to review blood test results and to agree any required action can substitute for visits, and home visits for blood tests and advice are permitted if more convenient (e.g. elderly patients). If home visits are undertaken this will be done in accordance with the University of Nottingham fieldwork guidelines. If the nurse requires any advice concerning treatment strategy (e.g. in patients with serious or multiple co-morbidity, taking multiple drug treatments, or experiencing side-effects) this will be offered by Academic Rheumatology ([name] or, in his absence, another designated Rheumatologist – [name], [name] or [name]). All contacts with the patient (practice visit, home visit, telephone call) and for doctor advice will be logged (date, duration) for subsequent cost effectiveness analysis. Participants will be given a diary to keep during the 2 year study period in which they will record the date and duration of acute attacks of gout.

### Assessment will involve:

**Enquiry:** age, sex, gout history (onset, acute attacks/frequency/sites affected/chronic symptoms), drug history (allopurinol/start date/dose, diuretics/duration; other drugs), family history comorbidities (most detailed first visit), completion of a QOL questionnaire (generic - SF36; and disease-specific - the gout assessment questionnaire (GAQ)) at the end of year one and again at the end of year 2. The questionnaires will take approximately 20 minutes to complete. Participants' blood pressure will also be checked at the end of year 2.

**Examination**: tophi (sites); height, weight (BMI).

**Investgations**: serum uric acid, GFR, creatinine.

If tophi are present, the maximum diameter of the longest tophus will be measured using a Vernier calliper and the total number and site of tophi will be recorded.

All investigations will only be undertaken to assist clinical assessment. Individuals participating in the study will receive a package of care based on current recommended quidelines.

# Page **17** of **29** Final version 8 –18 May 2015

Blood samples will be collected by the research nurses and taken to the Nottingham City Hospital laboratory for analysis. The samples will be destroyed following the NUH Trust's standard operating procedures.

All results will be discussed with the patients. Any abnormal findings, unrelated to the diagnosis of gout, will be discussed with the patient and their GP informed to enable appropriate action.

### **B] Control/Standard Care arm**

Participants randomised to this group will have one consultation appointment with the research nurse. At this appointment they will be assessed by the nurse (identical enquiry, examination and investigations as above) and be provided with the Arthritis Research UK gout information booklet and a diary to prospectively document their acute attacks (frequency, duration, medical advice sought, medications taken, absence from work). The discussion will focus on the management of acute attacks and not on long-term management. In addition, they will be asked to provide a blood sample to check their SUA level at baseline, 12 months and 24 months, and complete a QOL questionnaire at 12 months (a new diary will be given at this point) and 24 months. This standard care group of participants will remain under the care of their general practitioner.

### Collection of additional blood sample (optional)

All participants will also be invited to give a 10ml sample of blood for use in future gout research. This will include 1] genetic research to help identify genes that associate with gout development and severity and 2] study of metabolic changes (particularly biomarkers that associate with cardiovascular risk) that accompany a change in serum uric acid over time. The samples for genetic testing will be taken at baseline and those for metabolic biomarker research will be taken at baseline and one and two years. These time points allow the additional blood to be taken at the time venepuncture will be undertaken for the main study and therefore will not require an additional venepuncture. It will be explained to patients that participation in this additional genetic and metabolic research is optional and is not required as part of the main Arthritis Research UK Gout Treatment Trial and is covered in a separate optional clause on the consent form.

### **HUMAN TISSUE**

Gout Treatment Trial blood samples will be collected by the research nurses during the appointments undertaken at the GPs surgeries and transported, by the research nurse, to the Nottingham City Hospital laboratory for analysis. Samples will not be retained for future research purposes and will be destroyed by the Nottingham City Hospital laboratory, following the Nottingham University Hospital Trust's standard operating procedures.

If the participant agrees to provide an additional sample for future genetic and metabolic biomarker studies related to gout, these samples will be stored in the Clinical Sciences Building, Nottingham City Hospital and stored within the Research Tissue Bank for future

Page **18** of **29** Final version 8 –18 May 2015

research (DI [name] Licence Number 12265) if participants are agreeable and sign the optional clause on the consent form.

Only de-identified samples will be sent to third parties including close collaborating research groups and/or commercial companies who will undertake some of this analysis.

### LABORATORY ANALYSES

Bloods collected for the Gout Treatment trial will be transported to the laboratory at the Nottingham City Hospital for analysis. The bloods will be tested for serum uric acid levels, GRF and liver function (if required).

Bloods collected for future genetic and biochemical markers studies will be stored in the Clinical Sciences Building at the Nottingham City Hospital. Whole blood will be sent to a specialist company for DNA extraction and processing. The DNA will be used to identify genes that identify with gout development and severity. Biochemical marker measurements in sera will be carried out using either radioimmunoassay specific equipment for ELISAs and/or magnetic resonance spectroscopy for metabolite detection.

### Compliance

This is a complex intervention. However, compliance with respect to the nurse intervention will be judged by attendance for appointments, and by completion of the end of study questionnaire. Compliance to prescribed ULT will be judged by discussion with the participants, by their prescription requirements and by the results of the serial SUA.

### Criteria for terminating trial

It is not envisaged that circumstances will arise that require termination of the trial. The nurse intervention reflects recommended best practice which includes prescription of available licensed ULT.

### MONITORING STUDY PARTICIPANTS SUITABILITY TO CONTINUE IN THE STUDY

Prior to contacting participants in the RCT standard care arm, at one and two years, the GP surgeries will be provided with a list of participants in these groups and asked to check their records to ensure that patients are still registered with surgery, living at the same address and are suitable to be contacted. If this is not feasible, the Health and Social Care Information Centre or other central UK NHS body will be contacted to confirm the contact address and health status of patients participating in the trial. As regular contact will be maintained with participants in the RCT Nurse Intervention arm it is envisaged that participants/family members will keep the study team informed. If there is any reason to believe that an individual status may have changed, e.g. no reply to correspondence, telephone calls or non-attendance for appointments the GP surgery will again be contacted.

### **STATISTICS**

### Methods

The trial statistician ([name]) will oversee the data management, evaluation and analyses. The database will be developed in collaboration with the CTU using access and analysed using SPSS. SUA will be analysed at baseline, 12 months and 24 months. Comparison will be undertaken between the nurse led intervention and control at each observational point. There will be no interim analyses for efficacy or safety. Intention to

Page **19** of **29** Final version 8 –18 May 2015

treat (ITT) analysis will be undertaken to compare treatment effects between groups. Multilevel models will be used for any missing outcome measures. Chi-square test will be used for dichotomous or categorical data and ANOVA test will be used for continuous variables. Adjustment will be made for baseline co-variables as appropriate. Cost per QALY will be estimated from the SF6D and the direct and indirect costs related to gout and its management.

### Sample size and justification

### Sample size:

512 participants will be recruited for the RCT (this allows a 10% drop out over the 2 year period).

### Power calculations:

Information that includes SUA on community-derived patients with gout is sparse. However, detailed information on frequency of attacks, treatment, SUA and quality of life is available for 250 gout patients from 17 practices in Nottingham (5, 11). In this survey: 30% of patients were on ULT; the rate for acute attacks in the previous year was 32% for patients on ULT and 57% for patients on no ULT; mean SUA was 318  $\mu$ mol/L in those taking ULT compared to 434  $\mu$ mol/L in those not taking ULT; and 23% of those taking ULT had a SUA >360  $\mu$ mol/L, compared to 75% of those not on ULT. For quality of life (SF36) overall mean and SD for those on ULT was 16.41 (2.81) compared to 15.67 (3.05) for those not on ULT, giving a pooled SD of 3.09 and a mean difference of 0.7 between groups (the latter is used as a proxy of effect size d).

According to these results, we have estimated the following sample size requirements, to achieve 90% power at 0.05% significance level, for each outcome:

- reduction in frequency of acute attacks in final year a sample size of 90 is required for each arm
  - reduction in SUA below the therapeutic target a sample size of 70 patients is required for each arm
- quality of life a sample size of 233 is required for each arm (80% power at 0.05% significance level

Allowing a 10% drop-out rate over the 2 years, this requires a total of **512 patients** (233 plus 23 dropouts in each arm) to provide adequate power for the primary outcome and for 2 of the key secondary outcomes. There are no data on changes in GAQ in response to treatment, but being a disease-specific instrument, we assume that the GAQ will be more sensitive to change than the SF36 and that a total size of 796 will be adequately powered for this outcome.

The total number of GP practices in Nottinghamshire is 170 and the estimated number of registered patients with gout is 10,720 (i.e. an average of 65 patients per GP). A questionnaire will be sent to all patients (unless they have an exclusion criterion) to detect eligible patents. A random sample of those eligible will be selected using the simple random selection after the consent to the trial.

Page **20** of **29** Final version 8 –18 May 2015

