### **SYNOPSIS**

Title	Nottingham Gout Treatment Trial. Phase 2: Two Year Randomised Controlled Trial of a Nurse Led Package of Care		
Acronym	None		
Short title	Nottingham Gout Treatment Trial – Phase 2		
Chief Investigator	[name]		
Objectives	To determine in community-based patients with untreated or under treated gout the effectiveness and cost effectiveness of a nurse-led complex intervention that reflects recommended best practice (including urate lowering therapy (ULT) to reduce serum uric acid (SUA) levels to <360 µmol/l).		
Trial Configuration	Randomised, parallel group controlled trial comparing nurse led intervention with "standard" (GP led) care over a 2 year period  Multicentre study within the East Midlands and South Yorkshire (EMSY) Region.		
Setting	Primary Care, EMSY Region		
Sample size estimate	RCT: The sample size was estimated according to both primary and secondary outcomes. To achieve 90% power at 5% significant level (2-tailed), the sample size needed are: 70 patients for each group for reduction in SUA (primary outcome); 90 patients for each group for reduction in frequency of acute attacks in the final year, and 233 patients for each group for quality of life (QOL). Allowing a 10% drop-out rate over the 2 years, this requires a total of 512 patients (233 plus 36 dropouts in each arm) to provide adequate power for the primary outcome and for the 2 key secondary outcomes.		
Number of participants	Nurse intervention (RCT) – 256 Standard care (RCT) – 256		
Eligibility criteria	All – Adults aged 21 and over with GP diagnosis gout, confirmed following telephone interview to ensure that participants fulfil ACR criteria for gout.  Nurse intervention and standard care groups (RCT) – at least one acute attack of gout in the last year.		
Description of interventions	Nurse intervention arm – package of care based on best practice, including full information concerning nature and prognosis of gout, addressing illness perceptions of gout and possible barriers to care,		

Page **4** of **29** Final version 8 –18 May 2015

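### The SF36 sample size of 233 per arm, which sets the total of 512, is given 90% power in one place and 80% in another, and the plan's inputs support neither.

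*Supplement*

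**What the plan says.** In the current protocol (version 8), the synopsis opens its sample size estimate with "To achieve 90% power at 5% significant level (2-tailed), the sample size needed are", and the list that follows includes "233 patients for each group for quality of life (QOL". It then says that "this requires a total of 512 patients (233 plus 36 dropouts in each arm".

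The section Power calculations begins with "to achieve 90% power at 0.05% significance level, for each outcome", but its quality-of-life line reads "quality of life a sample size of 233 is required for each arm (80% power at 0.05% significance level". That section does not say whether the test is one- or two-sided. It reaches 512 as 233 plus 23 dropouts per arm.

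The inputs come from a local survey of 250 gout patients, 30% of them on urate-lowering therapy (ULT). The SF36 means and SDs are "16.41 (2.81) compared to 15.67 (3.05) for those not on ULT", "giving a pooled SD of 3.09 and a mean difference of 0.7 between groups". For the Gout Assessment Questionnaire (GAQ), the plan assumes that "a total size of 796 will be adequately powered for this outcome".

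The other two outcomes need 70 and 90 per arm, so the SF36 figure determines the size of the trial.

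**The concern.** One sample size cannot have 80% and 90% power for the same effect under the same test. Since 233 drives the total, its stated power should at least follow from the inputs printed beside it. The pooled SD also looks wrong on sight, because it is larger than both SDs that it is meant to pool.

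The stake is how the SF36 result will be read. The protocol's background section calls evidence of improved quality of life the one thing missing for its planned policy submission. It also claims adequate power for this outcome. A non-significant SF36 comparison would then be taken to come from a trial with 80–90% power, when the documents do not show that.

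**Working it through.** **Inputs.** From Power calculations: means 16.41 and 15.67, SDs 2.81 and 3.05, stated difference 0.7, stated pooled SD 3.09, 30% of 250 on ULT, dropout 10%. From the synopsis: two-sided 5%, 256 per arm. The 0.05% in the body is read as 5%, to agree with the synopsis.

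**Trying to reproduce 233.** Formula: n per arm = 2(z_α + z_β)²(SD/difference)².
- Two-sided 5%, 0.7 and 3.09: 2 × (1.960 + 0.842)² × (3.09/0.7)² = 305.9, so 306 for 80% power. For 90% it is 410.
- To be right two-sided, 233 would need a standardised difference of 0.260 for 80% or 0.300 for 90%. Neither value is derived in the plan. The printed inputs give 0.7/3.09 = 0.227.
- One-sided 5% with a standardised difference of 0.23 gives 233.7 for 80% power. For 90% it gives 323.8, close to the 326 of the previous protocol version. A one-sided calculation is therefore the likely source, but this is inference. It conflicts with the two-tailed test in the synopsis.

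**Checking the pooled SD.** A pooled variance is a weighted mean of the two group variances, so the pooled SD must lie between 2.81 and 3.05.
- Weighted 30/70: √[(74 × 2.81² + 174 × 3.05²)/248] = 2.98.
- Equal weights: √[(2.81² + 3.05²)/2] = 2.93.
- Adding the between-group variance as well: √(2.98² + 0.3 × 0.7 × 0.74²) = 3.00, still below 3.09.

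The difference between the means is 16.41 − 15.67 = 0.74.

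**Power, two-sided 5%, unadjusted.** Power ≈ Φ[(difference/SD) × √(n/2) − 1.96].

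| Difference / SD | n for 80% | n for 90% | Power at 233 | Power at 230 |
|---|---|---|---|---|
| 0.70 / 3.09 (printed) | 306 | 410 | 68.6% | 68.1% |
| 0.74 / 3.09 | 274 | 367 | 73.4% | 72.9% |
| 0.74 / 2.98 | 255 | 341 | 76.4% | 75.9% |
| 0.74 / 2.93 | 247 | 331 | 77.8% | 77.3% |

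For the first row at 233: (0.7/3.09) × √116.5 = 2.445, and Φ(2.445 − 1.960) = Φ(0.485) ≈ 0.686. The t-test changes these powers by about 0.2 points. One-sided, power at 233 still does not exceed 86% in any row, so 90% fails either way.

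**Dropout arithmetic.** Synopsis: 2 × (233 + 36) = 538, not 512. The 36 belongs to the previous version's 326 + 36 = 362 per arm. Body: 2 × (233 + 23) = 512, which is consistent. Ten per cent loss from 256 leaves 230.4, not 233, a matter of about half a point of power.

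**The case against.** The strongest reply is that these are powers for a plain two-group comparison at one time point, whereas the plan is not confined to that. The protocol allows adjustment for baseline covariates, and the analysis plan puts baseline, 12 and 24 months into one multilevel model. Adjusting for baseline multiplies the SD by √(1 − r²), where r is the correlation between baseline and 24-month SF36. At an assumed r of 0.5 and 230 per arm, power is 80% with 0.7/3.09 and 87% with 0.74/2.98. On the corrected inputs, 80% needs 255 per arm and 256 are randomised, so the shortfall comes only from dropout and is about 4 points.

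This stands as far as it goes. A reader might infer that the trial's true SF36 power is about 70%. The documents do not support that, because it is an unadjusted figure on the least favourable inputs. They do not support the higher figures either: they give no correlation, the sample size uses none, and the analysis plan's covariate list does not name baseline SF36.

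A reader might also argue that power is lower still because some controls will be on ULT. The documents give no firm basis for putting a number on that. It would also mean treating a cross-sectional survey contrast as a treatment effect.

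Several of the faults are editorial: the 36 dropouts, the 0.05%, and 0.7 for 0.74. The remark that the raw difference stands in for d is loose wording and was not the calculation, since d = 0.7 would need only about 33 per arm for 80%.

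**Conclusion.** The point holds for what the plan states. The 233 per arm carries two incompatible powers, and neither follows from the plan's inputs under an unadjusted two-sided 5% test. Against stated powers of 80% and 90%, the printed inputs give about 69% and corrected inputs about 76–78% (68% and 76–77% after dropout). The printed pooled SD of 3.09 cannot be right, the synopsis's dropout sum does not give 512, and the GAQ claim rests on 796 patients, which this trial will not have.

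The result assumes the survey contrast as the effect size and two-sided testing, the only sidedness that the documents state. It does not show that the trial is underpowered overall. SF36 is a secondary outcome, and the primary outcome's stated requirement of 70 per arm is well below 230. This should be fixed, but it does not threaten the main conclusion.

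**What to change.** Keep 512 and change the wording:

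- In the synopsis and in Power calculations, state one SF36 power, labelled unadjusted and two-sided 5%: difference 0.74, pooled SD 2.98, 230 evaluable per arm, about 76%.
- Remove the 90% claim as it applies to quality of life, both in the synopsis and in the lead-in to the list in Power calculations.
- Correct 36 dropouts to 23 in the synopsis, and 0.05% to 5% in the body.
- Delete the sentence that rests GAQ power on 796 patients.
- Name baseline SF36 as a covariate in the SF36 analysis, either within the analysis plan's multilevel model or in an ANCOVA expressly reconciled with it.
- Give any adjusted power only as a range over assumed baseline correlations. With 0.74/2.98 and 230 per arm, for example, it is 83–91% for correlations of 0.4–0.6.

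The cost is protocol and analysis plan text and a less favourable stated power. No extra patients or data are needed, since SF36 is already collected at baseline.
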